# **Study Synopsis**

OBJECTIVE	The objective of the SECURE Study is to actively gather additional information on the use of the CanGaroo ECM ® Envelope in a post market observational study.	
STUDY POPULATION	1000 subjects who have received CanGaroo ECM ® Envelope for an implantable electronic device placement.	
INDICATIONS FOR USE	CanGaroo ECM ® Envelope is intended to securely hold an implantable electronic device to create a stable environment when implanted in the body. The devices that may be used with the CanGaroo ECM ® Envelope include pacemaker pulse generators, defibrillators, or other cardiac implantable electronic device.	
ENDPOINTS	
 
The endpoints will be defined as:
 
1. The proportion of subjects with CanGaroo ECM related adverse events.
 
2. The incidence of major pocket infection.
 
	
EXAMINATION SCHEDULE	In-office wound check, 4-6 week, 3 month and an additional visit occurring at any time point after 3 month visit following an implantable electronic device procedure utilizing CanGaroo ECM ® .	
CLINICAL Parameters	
 
The following clinical data will be collected at post-operative visits:
 
Informed Consent
 
Demographic information
 
Risk factors for infection
 
Implant procedure
 
Type of device implanted
 
Information on CanGaroo ECM
 
CanGaroo ECM related adverse events
 
Information on infections
 
	
ANALYSIS	Outcomes for the SECURE Study will be compared to data collected from the U.S. Healthcare Cost and Utilization Project family of databases and/or contemporary literature.	

## 1. Introduction and Rationale

Broader indications for the implant of cardiac implantable electronic devices (CIED), a higher prevalence of systolic heart failure and population aging are the main reasons for the continuous increase in the use of pacemakers, implantable cardioverter-defibrillators and devices for cardiac resynchronization therapy. The rate of infection is out of proportion to the increase in implantation rate. This is thought to be primarily due to the associated comorbities in CIED patients, the greater complexity of the devices, and the increased duration of procedures.

The CanGaroo ECM Envelope is a 'pouch' in which a cardiac implantable electronic device is placed prior to implantation to create a stable environment and to provide a barrier between the CIED and the soft tissue of the patient and a barrier from the CIED leads.

CorMatrix Cardiovascular, Inc. received FDA 510(k) premarket clearance for the CanGaroo ECM (K140306) on August 15, 2014. This post market observational study will evaluate the safety and effectiveness of CanGaroo ECM following an implantable electronic device procedure utilizing CanGaroo ECM. Specific data will be collected at the first post-operative visit.

## 2. Indication for Use

The CanGaroo ECM Envelope is intended to securely hold an implantable electronic device to create a stable environment when implanted in the body. The devices that may be used with the CanGaroo ECM Envelope include pacemaker pulse generators, defibrillators, or other cardiac implantable electronic device. The entire Instructions for Use (IFU) can be found in Appendix C.

# 3. Description

The CanGaroo ECM is constructed from a multilaminate sheet (4-ply) of decellularized, noncrosslinked, lyophilized extracellular matrix (ECM) derived from porcine small intestinal submucosa (SIS). SIS is a natural collagen construct derived from a select layer of tissue that is recovered from porcine small intestine. During processing, the inner and outer muscle layers of the intestine are removed, leaving an intact, decellularized, submucosa with a portion of the tunica propria layer attached to the inner surface. The CanGaroo ECM Envelope will be provided sterile and is intended for single use in a single patient only. Over time, the device will be reinforced by cellular infiltration and tissue growth that will integrate the CanGaroo ECM Envelope.

### 4. Prior Clinical Evaluations

ECM has been studied in previous prospective clinical evaluation, and a post-market clinical study is ongoing. The ECM for Pericardial closure has been studied in a randomized, prospective study to evaluate its ability to reduce the incidence of new onset atrial fibrillation; the ECM for Carotid Repair is under evaluation in a post-market study to capture and assess device performance data from subjects undergoing patch angioplasty of the carotid artery following carotid endarterectomy using the product per its FDA-cleared Indications for Use; and a post market study to capture additional information (RECON) from subjects undergoing a procedure requiring pericardial closure using the product per its FDA-cleared Indications for Use.

#### 4.1. Clinical Evaluation of the ECM Pericardial Closure Device

The ECM Pericardial Closure device was evaluated in a multicenter, prospective, randomized, controlled clinical study, to demonstrate the safety and effectiveness of the device to reduce the incidence of new onset postoperative atrial fibrillation by circumferentially reconstructing the normal pericardial anatomy following isolated, firsttime, coronary artery bypass grafting (CABG) procedures as compared to the control group subjects who did not undergo pericardial closure. Safety was to be established by demonstrating that the composite clinical event rate for the ECM group was not worse than the control group. Effectiveness was to be established by demonstrating a reduced incidence of new onset post-operative atrial fibrillation in the ECM group as compared to the control group. 440 patients at 15 U.S. sites were enrolled between December 2010 and November 2012 and randomized in a 1:1 ratio into either the ECM group (pericardial closure) or the control group (no pericardial closure). A blinded, independent core laboratory evaluated all arrhythmia data to determine if subjects met the effectiveness endpoints. A blinded, independent Clinical Events Committee adjudicated all safety endpoint events. Patients were evaluated at hospital discharge, 30 days and 270 days postoperatively. Subjects were adults (at least 18 years of age) with no prior history of atrial fibrillation or history of anti-arrhythmia drug treatment in the past three months and no implantable cardiac devices (i.e., cardiac resynchronization therapy devices with and without defibrillator capabilities [CRT-Ds and CRTs), implantable cardioverterdefibrillators [ICDs] and pacemakers) undergoing isolated, first-time CABG with a median sternotomy approach.

The primary effectiveness endpoint, superiority of the ECM over no pericardial closure for reduction in the incidence of new onset post-operative atrial fibrillation, was not met. The study results showed that the rate of new onset post-operative atrial fibrillation for the primary effectiveness endpoint was similar between the two groups, with a rate of 38.3% in the ECM group compared with 35.9% in the control group. The two secondary effectiveness endpoints, the rate of treated or sustained episodes of new onset postoperative atrial fibrillation (defined as a single episode that last 15 minutes or more) and the rate of treated episodes of new onset postoperative atrial fibrillation showed results were also similar between the two groups. The composite primary safety endpoint event rates for the ECM and control group were 3.9% and 3.7%, respectively. Using the protocol specified non-inferiority margin, 7.5%, the ECM was shown to be non-inferior to control for the primary safety endpoint (p<0.001). Therefore, the primary safety endpoint for the study was achieved. The composite secondary safety event rate was similar for the two groups (5.8% for the ECM group compared with 3.9% for the control group) demonstrating no significant increase in the rate of bypass graft failure in the ECM group compared with the control group.

Although the study failed to demonstrate a reduction in the incidence of new onset postoperative atrial fibrillation, the study demonstrated that the ECM for Pericardial Closure continues to be safe for its intended use, with no significant increase in the rate of bypass graft failure or cardiac tamponade compared with no pericardial closure.

#### 4.2 Post-market Clinical Evaluation of the ECM for Carotid Repair

Aziyo is currently conducting a post-market registry study for the ECM for Carotid Repair (Protocol No. 11-PR-1021). The objective of this registry is to capture and assess device performance data from subjects undergoing patch angioplasty of the carotid artery following carotid endarterectomy using the ECM for Carotid Repair per its commercial Indications for Use. This registry provides an ongoing post-market surveillance mechanism to document clinical outcomes on the use of the ECM for Carotid Repair. This is a multi-center, prospective, single-arm, post-market, observational registry of subjects receiving the ECM for Carotid

Repair for patch angioplasty following carotid endarterectomy procedures. This postmarket registry may involve up to ten U.S. clinical sites and up to 230 subjects. Data will be collected through the 24-month follow-up.

One-hundred and eighty-six patients are enrolled in the study and included in the interim analysis of the ECM for Carotid Repair registry. The data demonstrated that the rate of device related adverse events were consistent with the rates found in the review of the contemporary literature for patch angioplasty. Specifically, no unanticipated events were found and the rate of the events was as anticipated in the risk management plan. Of specific interest in the analysis was the rate of pseudoaneurysm, which was present in 2 (1.08%) of the 186 patients and compared favorably to the rates found in the literature (1.4% to 5%).

The mean carotid stenosis (maximum) at pre-operative was 84.8%. Mean change from baseline values were -56.8%, -57.9%, and -59.6% at the 1 to 3-month, 6-month, and 12-month follow-up evaluations. The mean carotid stenosis (minimum) at pre-operative was 71.7%. Mean change from baseline values were -63.9%, -61.2%, and -63.4% at the 1 to 3-month, 6-month, and 12-month follow-up evaluations.

As a result of this analysis and the directed and ongoing risk management activities, the overall residual risk of the ECM for Carotid Repair is determined to be acceptable.

# 5. Study Objectives

The objective of the SECURE Study is to actively gather additional information on the use of the CanGaroo ECM® Envelope in a post market observational study.

### Endpoints

The endpoints will be defined as:

- 1. The proportion of subjects with CanGaroo ECM related adverse events.
- 2. The incidence of major pocket infection.

Major infection will be defined as 1) superficial cellulitis in the region of the CIED pocket with wound dehiscence, erosion or purulent drainage, 2) deep incisional or organ/space (pocket) surgical site infection, 3) persistent bacteremia or 4) endocarditis. Minor CIED infections include any that do not meet the definition of a major CIED infection. Documentation will also be provided in the medical records.

# 6. Study Design

This is a multi-center post-market observational study. It is anticipated that up to 1000 subjects will be enrolled at up to 50 centers. Eligible candidates will be approached to ascertain interest in study participation at their initial follow up visit. If a subject is interested in participating and has had CanGaroo ECM used in their procedure, they will be asked to allow their physician to use their medical information from the procedure and four follow up visits. An informed consent will be provided to the patient and the patient will be asked to sign unless a Waiver of Documentation of Consent has been obtained. If a Waiver of Documentation of Consent is in effect, all elements of the approved informed consent will be provided verbally and the process will be documented in the subject study binder by the research staff for either method of consent.

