### 9. Study Procedures

Patients return for an in-office wound check, a 4-6 week, 3 month and any visit following the 3 month visit depending on the investigator's standard of care for follow up. If the subject is unable to return to the clinical site for all visits, the site may contact the subject or the referring physician to provide follow-up data to study site by telephone.

The following information collected and documented:

- Informed Consent
- Demographic information
- Risk factors for infection
- Implant procedure
- Type of device implanted
- Information on CanGaroo ECM
- CanGaroo ECM related adverse events
- Information on infections

All study-related data will be captured on a standardized Case Report Form. A copy of the Case Report Forms is provided in Appendix B. Case report forms will be sent to Aziyo via email or fax.

[name] Aziyo Biologics, Inc. [name] [contact] Direct Office [contact] Fax [contact]

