#### Serious Adverse Event (SAE)

A serious adverse event is defined as an event that: a) led to death, b) led to serious deterioration in health that either:

- 1) Resulted in life threatening illness or injury, or
- 2) Resulted in a permanent impairment of a body structure or body function, or
- 3) Required in-patient hospitalization or prolongation of existing hospitalization, or
- 4) Resulted in medical or surgical intervention to prevent life threatening illness or injury or permanent impairment to a body structure or a body function.

A planned hospitalization for pre-existing condition without a serious deterioration in health, is not considered to be a serious event.

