### 10.3 Possible Adverse Events

This study will capture events reported following the procedure and at follow up visits as reported by the PI and/or subject and from a review of medical records. The following device-related events have been identified as possible risks from the procedure:

- Allergic reaction to ECM
- Bleeding
- Calcification
- Fever
- Fibrosis
- Hematoma
- Infection
- Inflammation
- Seroma
- Undesired remodeling

There are no identified risks involved in participating in this post-market study.

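### Section 6 describes access to records from the procedure and four visits, and no stated procedure seeks infections treated between visits or elsewhere; missed events would lower the infection rate

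*Combined protocol and SAP*

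**What the plan says.** Section 6 (Study Design) is where the protocol describes what subjects are asked to permit. Of a subject who is interested and has received the envelope, it says "they will be asked to allow their physician to use their medical information from the procedure and four follow up visits". It does not mention unscheduled visits, hospital admissions or other providers' records. The four visits are set out in the Study Synopsis: "In-office wound check, 4-6 week, 3 month and an additional visit occurring at any time point after 3 month visit". Section 9 leaves the timing of the last one to local standard of care.

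Other sections describe how events reach the database:

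- Section 10.3 says events are captured "as reported by the PI and/or subject and from a review of medical records", with no restriction to particular visits.
- Section 10.2 requires serious and device-related events to reach the sponsor within 24 hours of the investigator becoming aware of them.
- Section 9 provides that, if a subject cannot return for all visits, "the site may contact the subject or the referring physician to provide follow-up data to study site by telephone".
- Section 12.1 has the sponsor review submitted data and discuss adverse events and infections with the site.

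The events at stake include serious ones. The major infection definition under Endpoints (Section 5) covers deep incisional and pocket infection, "persistent bacteremia or 4) endocarditis". The seriousness criteria in Section 10.1 include "Required in-patient hospitalization or prolongation of existing hospitalization". Section 12.3 requires the subject's approval before study-specific information is obtained. The consent form (Appendix A) and the case report form (Appendix B) are separate documents and were not available for this review.

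**The concern.** Both primary endpoints are simple proportions, so they depend on finding and classifying every event. The protocol's own definitions include events that can lead to admission or surgical intervention. The evidence needed to call such an event major or minor may then lie in that admission's record rather than in a routine visit note. If a site takes Section 6 as the limit of what it may use, and nothing requires it to ask about care received between visits, some of these events could go unrecorded or unclassified.

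Such a loss would act in one direction. A missed infection lowers the Endpoint 2 rate, and lowers the Endpoint 1 rate when the event is also device-related. Section 11 plans, if possible, to compare the infection rate with rates without the device from external databases or literature, so under-capture on the study side would make the device look better. The exact binomial interval describes sampling error and gives no sign of this. With up to 50 centers, differing readings of the permitted scope could also produce differing ascertainment.

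**Working it through.** **Visit count.** Wound check, 4-6 weeks, 3 months and one later visit make 1 + 1 + 1 + 1 = 4, which agrees with the four visits in Section 6. The gap is therefore in the care that falls between and after those visits. Section 10.2 still refers to one postoperative visit and Section 1 to data from the first such visit; both should be aligned at the same time.

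**Routes by which an infection treated between visits could be found.**

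- *Scheduled visit:* infection information is collected (Section 9), but the protocol text requires no question about interval admissions, antibiotics, pocket re-entry or device removal. After 3 months the interval has no fixed end.
- *24-hour reporting (Section 10.2):* not tied to a visit, but starts with investigator awareness. No procedure is given to create that awareness for care elsewhere.
- *Telephone contact (Section 9):* optional, and offered for subjects who cannot attend all visits. It may bring an admission to light but does not have to ask about one.
- *Chart review (Section 10.3):* unrestricted as written, but wider than the permission described in Section 6. No timing or facility is specified.
- *Data review (Section 12.1):* works on submitted data, so it cannot reveal an event that was never submitted.

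Each route can find an event. None actively looks for one treated outside the scheduled visits.

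**Size.** The plan gives no figure to reproduce. It states no expected infection rate, power or attrition, so everything below except N is an assumption.

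- N = 1000 (Section 6, upper limit).
- Share of major infections first treated outside a scheduled visit: *a* = 0.30 to 0.60 (assumed).
- Share of those that cannot be confirmed from visit notes: *b* = 0.20 to 0.50 (assumed).
- True major infections: 10 in 1000, or 1% (assumed).

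Loss = *a* × *b*. Low: 0.30 × 0.20 = 0.06. High: 0.60 × 0.50 = 0.30. Events lost: 10 × 0.06 = 0.6, up to 10 × 0.30 = 3. The expected observed rate falls from 1.0% to between 9.4/1000 = 0.94% and 7/1000 = 0.70%.

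**Effect on the planned interval.** Exact (Clopper-Pearson) 95% intervals for N = 1000:

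| Assumed true rate | Full capture | 80% capture | 50% capture |
|---|---|---|---|
| 1% | 10 events, 1.0% (0.48-1.83) | 8 events, 0.8% (0.35-1.57) | 5 events, 0.5% (0.16-1.16) |
| 2% | 20 events, 2.0% (1.23-3.07) | 16 events, 1.6% (0.92-2.59) | 10 events, 1.0% (0.48-1.83) |
| 3% | 30 events, 3.0% (2.03-4.26) | 24 events, 2.4% (1.54-3.55) | 15 events, 1.5% (0.84-2.46) |

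At 80% capture, a 20% loss that lies within the assumed range, every interval still contains the true rate. At 50% capture, which lies outside that range and is shown as a stress case, the interval excludes the true rate when it is 2% or 3%.

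**The case against.** The strongest reply is that Section 6 summarises the request to subjects and excludes nothing. The operative permission is the consent form, which may be broader, and the case report form may already ask about interval admissions. Both points stand. They make the fix conditional, but they do not close the gap in the protocol text.

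A reader might go further than the documents allow in several ways:

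- *That Section 6 permits these records and no others.* It carries no such restriction.
- *That Sections 6 and 10.3 contradict each other.* They differ in scope and need to be reconciled. Section 10.3 also speaks of follow-up visits, and its chart review could be read as confined to permitted records.
- *That a subject who is admitted and misses the next visit leaves no source, or that sites depend wholly on subject recall.* Telephone contact with the subject or referring physician, 24-hour reporting, chart review and sponsor follow-up with the site all remain. Capture may be incomplete; it is not absent.
- *That major infections commonly present at unscheduled admissions.* The documents define these events but do not say where they are diagnosed.

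It is also fair to say that the size calculation multiplies two assumed ranges and applies them to an assumed event count. Even its upper end, 0.70%, lies within the interval for 10 events in 1000 (0.48 to 1.83). That limits the severity but not the direction of the bias.

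**Conclusion.** The point holds as a gap in ascertainment and a mismatch in record scope. The permission described in Section 6 is narrower on its face than the chart review in Section 10.3. No stated procedure actively seeks infections treated at unscheduled visits or admissions, and the last follow-up interval is open-ended. Any resulting loss biases the major infection rate downward, and the device-related event rate where applicable. Other things equal, and unless the external source under-captures to a similar degree, this favours the device in the Section 11 comparison.

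The documents do not fix the size. The 0.6 to 3 lost events per 10 rest entirely on the assumptions shown, and no estimate is offered for Endpoint 1. At that scale the bias is modest beside the sampling error, but the planned analysis would not reveal it. This should be changed because the remedy is specific and cheap, not because a large bias has been shown.

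**What to change.** Reword Section 6 to cover relevant medical records from implant to last study contact, including unscheduled visits, admissions and CIED or pocket procedures at any facility, so that it matches Section 10.3. Make the same change in the consent form if it is equally narrow; if the form is already broader, align Section 6 with it.

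In Section 9, unless the case report form already does this, require the site at each contact to ask and record yes or no, with date and facility, for four things since the last contact:

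1. hospital stay;
2. antibiotics for the pocket;
3. pocket re-entry;
4. CIED or envelope removal.

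Obtain the corresponding record for each yes.

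The cost is an IRB amendment, a few case report form items, a small number of record requests, and possible re-consent of subjects enrolled under narrower wording. No visit or study procedure is added.

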# 7. Study Population

The study population will consist of any subject who has received the CanGaroo ECM® Envelope for an implantable electronic device placement. Subjects will be considered enrolled into the study once they have provided informed consent and completed the procedure using the CanGaroo ECM Envelope. Before any subject can be enrolled, the site must have IRB approval from a centralized IRB or their specific institution IRB for the protocol and Informed Consent Form to be used at that site and Waiver of Documentation of Consent, if applicable.

